### 1.2.9 Rationale for the Use of Saracatinib in Recurrent Osteosarcoma

There is a large body of in vitro data showing Src plays an important role in the motility of osteosarcoma cells, a function that can be abrogated by the use of Src inhibitors. More importantly, Src and other genes that are involved in the Src pathway are activated in 95% of patients with osteosarcoma. These data suggest that saracatinib represents a promising candidate for the treatment of patients with recurrence of osteosarcoma.

We propose to utilize a newly described type of study, coined a Phase II.5 study (35). Phase II.5 studies examine outcome differences using a one-sided 0.10 alpha level significance test, rather than the traditional value of 0.05. The benefits of this type of study include enrollment of a fewer number of patients, which is important since patients with recurrent osteosarcoma are rare. In addition, it is a randomized, placebo-controlled trial, thus precluding the need to compare to historical controls, which is important since patients with recurrent osteosarcoma have previously received many different treatment modalities. The purpose of this design is to provide a sufficiently large, controlled, comparative evaluation to determine whether a sufficient effect is noted. Although the results are not definitive, if merited, they can then be used to estimate the parameters to design a definitive subsequent trial.

The trial objective is to perform a randomized, double-blinded, placebo-controlled study to evaluate the addition of saracatinib to pulmonary metastasectomy, versus placebo and pulmonary metastasectomy, in patients with relapsed osteosarcoma, localized to the lung. Currently, patients who achieve a surgical second remission have a progression free survival rate of 33% at two years and an overall survival rate of 45% at three years. An important caveat to this statement is that these patients have received a multitude of

different treatments, including surgery alone, and/or radiation, and/or chemotherapy, and/or high dose chemotherapy with stem cell rescue. Therefore, historical data do not give a true indication of actual survival rates. This study will try to determine whether patients who receive saracatinib will experience a 60% relative increase in progression free survival. Secondary objectives will determine whether patients who receive saracatinib will experience a 56% relative increase in overall survival and an increase in the time to treatment failure. Any adverse event, including toxicity, disease progression and death, that result in discontinuation of either saracatinib or placebo will be considered a treatment failure. The randomized nature of this study will allow us to determine the actual survival rates in these two cohorts, thereby assessing the efficacy of saracatinib in this patient population. Forty-four patients will need to be randomized in each arm, for a total of 88 patients, over a 48-month accrual period. Follow-up for survival of the last patient randomized must continue for an additional year. Patients who recur in the lung while on-study and who are thought to be amenable to complete surgical resection will be unblinded. Those who were receiving placebo will be given the option of undergoing surgical resection. If fully resected, they will be given the option to begin oral therapy with saracatinib.

## 2 Eligibility Assessment and Enrollment

### 2.1 Eligibility Criteria

#### 2.1.1 Inclusion Criteria

Patients who have recurrence of osteosarcoma, localized to the lungs, who have had complete surgical removal of all lung nodules, are eligible for enrollment.

OR

Patients with suspected recurrence of osteosarcoma but have not had surgery are eligible for enrollment but will not be randomized until inclusion criteria (a) and exclusion criteria (b) are confirmed after surgery. If these are not confirmed, patient will be considered a screen failure and will not be randomized.

Other inclusion criteria are as follows:

- a. Histological diagnosis of osteosarcoma of the recurrent sample (histology types must be osteoblastic, chondroblastic, fibroblastic or telangiectatic). For patients enrolled prior to surgery, this criterion can be confirmed after consent, enrollment and surgical resection.
- b. Recurrence of osteosarcoma in the lung following standard chemotherapy including: adriamycin, cisplatin, ifosphamide and methotrexate (or provide justification why any of these agents were not received, for example, previous toxicity with methotrexate, or methotrexate not routinely given for adult patients)
- c. Age  $\geq 15$  and  $< 75$  years of age
- d. Weight  $\geq 34$  kg
- e. ECOG performance score of 0, 1 or 2 (0 = asymptomatic, 1 = symptomatic but fully ambulatory, 2 = symptomatic in bed  $< 50\%$  of the day)
- f. Adequate bone marrow function (ANC  $\geq 1500/uL$ , Hb  $\geq 9.0$  g/dL, platelets  $\geq 100,000/uL$ )
- g. Adequate renal function (serum creatinine  $\leq 1.5$  or a creatinine clearance  $\geq 50$  mL/min/1.73m^2)
- h. Adequate hepatic function (ALT/AST  $\leq 2.5X$  normal, total bilirubin  $\leq 2$  mg/dl with the exception of patients with Gilbert's syndrome)
- i. Adequate cardiac function (ECHO or MUGA with shortening fraction  $\geq 27\%$  or ejection fraction  $\geq 45\%$ ) and (EKG with QTc  $\leq 480$  msec)
- j. Negative pregnancy test for women of childbearing potential,  $\leq 7$  days prior to enrollment, and the willingness to use an acceptable method of contraception during participation in the study and for 3 months after the last dose

- k. Randomization must occur  $\leq 6$  weeks after complete surgical resection of all tumor nodules
- l. Informed consent: all patients, or their legal guardian if the patient is less than 18 years of age, must sign a document of informed consent indicating their awareness of the investigational nature and the risks of this study

### 2.1.2 Exclusion Criteria

- a. Presence of metastatic disease in other locations in addition to the lung
- b. Extensive disruption of the lung pleura by tumor. For patients enrolled prior to surgery, this criterion can be confirmed after consent, enrollment and surgical resection. This does not include solitary nodules that involve the lung pleura, but that have been completely resected, with no evidence of additional pleural involvement.
- c. Paget's disease
- d. Current use, or previous use within the specified time period, of medications that are potent inducers, inhibitors or substrates of CYP3A4, (see Section 4.5)
- e. Known hypersensitivity to other Src/Abl non-receptor kinase inhibitors
- f. Any evidence of interstitial lung disease (bilateral, diffuse, parenchymal lung disease)
- g. Any concurrent condition which in the investigator's opinion makes it undesirable for the patient to participate in the trial or which would jeopardize compliance with the protocol. These include conditions that are severe and/or inadequately uncontrolled, such as severe or worsening hepatic, respiratory and cardiac impairment.
- h. Myocardial infarction within one year prior to study entry
- i. Bleeding diathesis, resulting in symptomatic bleeding
- j. Pregnant women or breast-feeding or nursing women
- k. Any agent (chemotherapy, biological or investigational) administered  $\leq 28$  days prior to enrollment
- l. Unresolved toxicity  $\geq$  CTCAEv3 grade 2 (except alopecia) from previous agents

The reasoning for the above criteria is that patients who meet exclusion criteria a-c have an extremely poor five-year survival rate (3). Since some patients will meet one of the above criteria, it is possible that a true survival advantage with adjuvant saracatinib treatment may go undetected if the above patients are included.

## 2.2 Screening

For patients who are enrolled prior to surgery, if there is a significant change in a patient health status post-operatively, appropriate screening studies should be repeated based on the judgment of the treating investigator.

- History and Physical Examination
  - vital signs, weight, height, ECOG score
- Laboratory Studies (within 7 days prior to enrollment)
  - urine or serum pregnancy test (for females of childbearing potential)
- Laboratory Studies (within 14 days prior to enrollment)
  - white blood cell count with differential
  - hemoglobin and hematocrit
  - platelet count
  - prothrombin time, partial thrombin time, INR
  - sodium, potassium, chloride, bicarbonate, blood urea nitrogen, creatinine, glucose
  - calcium, magnesium, phosphorus
  - ALT, AST, total bilirubin, direct bilirubin
  - alkaline phosphatase, lactate dehydrogenase, total protein, albumin
  - urinalysis
  - urine or serum pregnancy test (for females of childbearing potential)
- Functional Studies (within 14 days prior to enrollment)
  - EKG
- Radiographic Studies (within 6 weeks prior to definitive resection or within 6 weeks prior to randomization)
  - Thoracic CT scan with contrast (unless patient cannot tolerate contrast ) \*/\*\*
  - Bone scan \*\*
- Functional Studies (within 28 days prior to enrollment)
  - echocardiogram or MUGA
  - creatinine clearance (if serum creatinine is >1.5)

\* The thoracic CT scan must be performed at a slice thickness of 5 mm or less. If there is any suspicion of interstitial lung disease, the patient must undergo high-resolution CT imaging to exclude interstitial lung disease. Any evidence of interstitial lung disease will make the patient ineligible for the study (see Exclusion Criteria in Section 2.1.2.f). The suggested parameters for the high-resolution thoracic CT scan are as follows: position (supine), slice thickness ( $\leq 1.25$  mm), slice spacing (10 mm), start location (10 mm below the apices), end location (10 mm above the costophrenic angles).

\*\* There will be instances when patients have very small indeterminate nodules on the CT scan. Sometimes it will be difficult to determine if these are tumor nodules or not. For the purposes of this protocol, the oncologist, radiologist and surgeon will have to use their best judgment to decide if the patient is fully resected of tumor. The same applies for nonspecific uptake on bone scans.

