## 2.3 Patient Enrollment

[figure not shown]
A signed informed consent document will be obtained prior to entry onto the study. Following consent, patient information is entered in the eCRF database. All patients must have histological verification of recurrent osteosarcoma in the lung prior to randomization. A copy of the pathology report documenting histologic confirmation should be sent to the SARC RPM prior to randomization.

Enrollment will be centrally managed by the trial coordinating center, SARC. Patient data will be entered electronically by the participating institutions through the study website:

<https://velos.med.umich.edu/eres/jsp/ereslogin.jsp>

Each patient will be assigned a patient identification number automatically following enrollment. Patients can be enrolled at any time of the day, any day of the week, via the website.

Once the patient has undergone complete surgical resection and the institutional PI determines that all of the criteria for inclusion have been met per protocol Section 2.1, the eligibility CRF will be completed in the database. The patient can then be randomized.

Patients will be registered and then stratified based on the number of recurrences (FIRST versus SECOND versus THIRD or MORE) and the number of recurrent nodules (ONE or TWO versus THREE or MORE).

SARC will possess separate randomization sheets for each stratum. Patient treatment assignment will be kept confidential and will not be shared with the treating physician(s) or any other site team staff involved in the care of the patient, except in the event of a medical emergency where unblinding is necessary to ensure patient safety (See Operation Manual for details), or at the time of recurrence if the recurrence is in the lung. (See Section 7.4.2).

Any questions regarding eligibility or the randomization process can be addressed to the SARC Operations Office:

SARC Research Project Manager  
[name]  
[name]  
[name]  
[name]  
[contact]  
[contact]  
Email: [contact]

SARC, the study Principal Investigator and the Principal Investigators at each participating institution will have access to this website to review data regarding this clinical trial.

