### 3.2.3 Regimen for Patients Who Have Been Fully Resected

Patients who had resection of all tumor nodules at the time of their biopsy will be eligible for randomization after definitive histological diagnosis of recurrent osteosarcoma. Once the treating physician decides that the patient is able to tolerate oral therapy, the patient will be randomized to either the saracatinib arm or the placebo arm. Following randomization, tablets will be dispensed by the hospital pharmacy.

Cycle 1 Day 1 must commence no later than 6 weeks after the time of the definitive metastasectomy. Patients who cannot commence oral therapy within these time frames will be removed from the study.

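### The only required pregnancy test is tied to enrolment: it can be 49 days old at the first dose, or older if enrolment precedes surgery, and no new test is stated before cross-over to saracatinib

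*Combined protocol and SAP*

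**What the plan says.** **The test.** Section 2.2 places a urine or serum pregnancy test under "Laboratory Studies (within 7 days prior to enrollment". The same test appears again in the 14-day list of that section, also counted back from enrolment. Inclusion criterion j requires a negative result no more than 7 "days prior to enrollment, and the willingness to use an acceptable method of contraception during participation in the study". Appendix A has a single mark for the test, in the screening column. The pre-treatment row in section 3.4 calls for laboratory tests, but the list that defines them contains no pregnancy test.

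**Enrolment and first dose.** Section 3.2.2 separates enrolment from randomization, and section 2.1.1 lets patients with suspected recurrence enrol before surgery. Those patients "will not be randomized until inclusion criteria (a) and exclusion criteria (b) are confirmed after surgery"; criterion j is not among the items named. Section 3.2.3 then says "Cycle 1 Day 1 must commence no later than 6 weeks after the time of the definitive metastasectomy", and sections 3.2.4 and 3.2.5 repeat the limit.

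**Cross-over.** Section 3.2.6 lets a placebo patient with a resectable lung recurrence start saracatinib within 6 weeks of reoperation. Neither that section nor section 7.4.2 mentions a pregnancy test.

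**Safeguards.** Exclusion j bars "Pregnant women or breast-feeding or nursing women". Section 4.3 requires contraception and removal from the study if pregnancy occurs. After surgery, if health status has changed significantly in a patient enrolled beforehand, "appropriate screening studies should be repeated based on the judgment of the treating investigator". Randomization follows once "the institutional PI determines that all of the criteria for inclusion have been met per protocol Section 2.1".

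**The concern.** A pregnancy test before an investigational drug is meant to show that the patient is not pregnant when exposure begins. Here it shows her status at enrolment, and the protocol deliberately allows surgery and recovery to come between enrolment and dosing. A pregnancy too early to detect at enrolment, or one that follows a contraceptive failure, could go unrecognised at first exposure. No treatment cycle has a scheduled test that would pick it up later.

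Cross-over is the wider gap. A placebo patient's first exposure to saracatinib comes only after recurrence and a further operation, yet her one required test dates from her original enrolment.

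The stake is participant safety. Section 4.3 reports reduced embryonic survival and fetal malformations in rodents at doses comparable with or below human levels, and says effects on the human fetus are unknown. Eligibility starts at age 15.

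**Working it through.** The protocol states no figure for the age of the test at dosing, so there is none to reproduce. The check is date arithmetic.

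**Inputs from the protocol**
- Test to enrolment: at most 7 days (criterion j, section 2.2). Criterion j is stricter than the 14-day listing, so 7 is used. The 14-day listing alone would give 14 + 42 = 56 days.
- Definitive resection to Cycle 1 Day 1: at most 6 weeks = 42 days (sections 3.2.3 to 3.2.5).
- Cross-over reoperation to first saracatinib dose: at most 42 days (section 3.2.6).
- Placebo treatment: 13 × 28 = 364 days.

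**Illustrative values, not in the protocol**
- d = days from complete resection to enrolment.
- t = days from enrolment to first operation; s = days between staged operations.
- r = days from first placebo dose to recurrence.

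**1. Enrolled on or after the day of complete resection.** Maximum age at first dose = 7 + (42 − d) = 49 − d.

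| d | Maximum age (days) |
|---|---|
| 0 | 49 |
| 14 | 35 |
| 28 | 21 |
| 42 | 7 |

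For these patients 49 is a ceiling, and the true gap may be only days.

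**2. Enrolled before surgery.** Maximum age = 7 + t + s + 42 = 49 + t + s.
- t = 14, s = 0: 63 days.
- t = 14, s = 28: 91 days.

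Sections 3.2.4 and 3.2.5 ask for prompt surgery, with only the second staged side left to the surgeon's timing. Section 2.2 requires CT and bone scan within 6 weeks before definitive resection or randomization. These keep t and s short in practice, but none sets a numeric limit on the age of the pregnancy test.

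**3. First cross-over dose.** The minimum age is r. It is reached only if test, enrolment and first placebo dose share one day, and recurrence, reoperation and first saracatinib dose share another. With enrolment on the day of resection and reoperation on the day of recurrence, the age can reach 7 + 42 + r + 42 = r + 91.

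| r (days) | Taken as | Age of test (days) |
|---|---|---|
| 21 | first scheduled CT, week 3-4 | 21 to 112 |
| 84 | end of cycle 3 | 84 to 175 |
| 364 | end of treatment | 364 to 455 |

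The upper values rise with enrolment before surgery, or with later or staged reoperation. The lower values are floors that real scheduling would exceed.

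**4. Does any safeguard force a new test?**
- Contraception: a separate requirement. The protocol asks for both contraception and a test.
- Exclusion j: concerns status and sets no test date.
- Repeat screening (section 2.2): depends on a significant health change and on judgment, and covers only patients enrolled before surgery.
- Eligibility check (section 2.3): criterion j is already met by the enrolment test.
- Scheduled visits (section 3.4): 14 visits with history and physical from week 1 through month 12, none with a pregnancy test.

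None does.

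**The case against.** The strongest reply is that anchoring to enrolment is a legitimate design choice. The protocol gives no period for which a test stays valid before dosing, so calling the test expired would import a standard the documents do not contain. It also has layered protection: mandatory contraception, exclusion of pregnant women, removal on pregnancy, prompt surgery, an imaging window and frequent clinical review. This stands in part. It limits the claim to the age of the test and the lack of a required repeat, but it does not supply a repeat.

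A reader might infer that cross-over patients go more than a year without clinical review. The documents do not support that. Visits are frequent on placebo, and age of the test is not time without review. Section 3.4 also requires a pre-treatment evaluation for enrolled patients without excluding cross-over treatment, so whether a cross-over pre-dose visit is required is ambiguous. If it is, the visit still contains no pregnancy test.

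A reader might also infer that women will be dosed untested. The text shows only that no later test is stated in it. The protocol defers operational detail on randomization, unblinding and drug supply to the Operations Manual, which was not available, so a test required there cannot be ruled out.

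**Conclusion.** The point holds for the protocol text reviewed. A site can follow it exactly and give the first dose on a test up to 49 days old when enrolment is on the day of resection. The age is less with later enrolment, and more, without a stated numeric limit, with enrolment before surgery. At the first cross-over dose the required test is always at least as old as the patient's time on placebo, and that minimum needs no assumption about surgical scheduling. The 49 days rests only on the protocol's 7-day and 6-week windows; the longer figures rest on the illustrative intervals.

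The documents do not say how many patients enrol before surgery, cross over or are women of childbearing potential, so the number affected is unknown. Power and the primary analysis are unaffected. This is a cheap safety improvement that should be made, not a flaw in the trial's inference.

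**What to change.** Keep criterion j and the enrolment test. Delete the duplicate pregnancy-test entry in the 14-day list of section 2.2.

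Add a separate dosing precondition to sections 3.2.3 to 3.2.5, the pre-treatment row of section 3.4 and the pre-dose column of Appendix A. It should require, for women of childbearing potential, a negative urine or serum pregnancy test within 7 days before Cycle 1 Day 1, with the clinical team confirming the window. Do it before randomization where possible and repeat it if the start slips. The enrolment test counts if it falls in the window. In section 3.2.6, require the same test within 7 days before the first cross-over dose, done before saracatinib is dispensed.

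This should be a dosing precondition and not a re-dated criterion j. Section 2.3 needs all inclusion criteria settled before randomization, and a criterion tied to a later dose may not be confirmable then. Moving the anchor could also drop the enrolment test. There is precedent: the phosphorus work-up in section 3.3.3 and the drug washouts in section 4.5 are already tied to the start of oral therapy.

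With the change, the maximum age at either first dose is 7 days. The cost is wording in seven places (sections 2.2, 3.2.3, 3.2.4, 3.2.5, 3.2.6, 3.4 and Appendix A) and one or two simple tests per woman of childbearing potential. There is also a small chance that a repeat test is positive after randomization, leaving a randomized but untreated patient (one is 1/88 = 1.1%). Section 3.2.3 says "Once the treating physician decides that the patient is able to tolerate oral therapy, the patient will be randomized", and sections 3.2.4 and 3.2.5 set the same condition, so testing before randomization should keep this rare.

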## 2.3 Patient Enrollment

[figure not shown]
A signed informed consent document will be obtained prior to entry onto the study. Following consent, patient information is entered in the eCRF database. All patients must have histological verification of recurrent osteosarcoma in the lung prior to randomization. A copy of the pathology report documenting histologic confirmation should be sent to the SARC RPM prior to randomization.

Enrollment will be centrally managed by the trial coordinating center, SARC. Patient data will be entered electronically by the participating institutions through the study website:

<https://velos.med.umich.edu/eres/jsp/ereslogin.jsp>

Each patient will be assigned a patient identification number automatically following enrollment. Patients can be enrolled at any time of the day, any day of the week, via the website.

Once the patient has undergone complete surgical resection and the institutional PI determines that all of the criteria for inclusion have been met per protocol Section 2.1, the eligibility CRF will be completed in the database. The patient can then be randomized.

Patients will be registered and then stratified based on the number of recurrences (FIRST versus SECOND versus THIRD or MORE) and the number of recurrent nodules (ONE or TWO versus THREE or MORE).

SARC will possess separate randomization sheets for each stratum. Patient treatment assignment will be kept confidential and will not be shared with the treating physician(s) or any other site team staff involved in the care of the patient, except in the event of a medical emergency where unblinding is necessary to ensure patient safety (See Operation Manual for details), or at the time of recurrence if the recurrence is in the lung. (See Section 7.4.2).

Any questions regarding eligibility or the randomization process can be addressed to the SARC Operations Office:

SARC Research Project Manager  
[name]  
[name]  
[name]  
[name]  
[contact]  
[contact]  
Email: [contact]

SARC, the study Principal Investigator and the Principal Investigators at each participating institution will have access to this website to review data regarding this clinical trial.

For patients at the National Cancer Institute, in addition to the required enrollment procedure described above, the following are also required prior to initiation of therapy. Patients must register with the NCI Central Registration Office (CRO, [contact], [contact]). A completed eligibility checklist and a signed consent form must be on file prior to entry onto the study. Research nurses in the Pediatric Oncology Branch will facilitate this process.

